Appendix 6.	Classification of Contraceptive Methods.....	86

1. Synopsis

Title of Study:

A Randomized, Phase 3, Open-label Trial Comparing the Effect of Tirzepatide Once Weekly Versus Titrated Insulin Glargine on Glycemic Control in Patients with Type 2 Diabetes on Metformin with or without a sulfonylurea.

Rationale:

Type 2 diabetes mellitus (T2DM) is a metabolic condition characterized by impaired glycemic control caused by increased insulin resistance and progressive beta-cell failure and consequently inadequate insulin secretion. The diabetes therapy usually starts with lifestyle and diet changes followed by 1 or more oral medications. When oral antihyperglycemic medications (OAMs) are insufficient to reach target glycemia, injectable therapies are added to them. For most patients, a glucagon-like peptide-1 (GLP-1) receptor agonist should be the first choice, ahead of insulin. Basal insulin alone is the most convenient initial insulin regimen and can be added to metformin and other oral agents (American Diabetes Association [ADA] 2019). Adequately titrated glargine therapy, in combination with oral OAMs, frequently achieves the target glycemic level. Glargine therapy, however, is frequently associated with weight increase and eventual hypoglycemia.

Injectable incretin-based treatments (e.g., GLP-1 receptor agonists) are recommended as first injectable used in combination with OAMs to achieve and maintain glucose control (ADA 2019). While associated with lower risk for hypoglycemia and either weight neutral or weight loss effects, current preparations are directed at a single molecular target (GLP-1 receptors) and provide dose-dependent glucose-lowering effects, which can be limited by gastrointestinal (GI) tolerability (Nauck 2016).

Tirzepatide is a once-weekly dual GIP/GLP-1 receptor agonist. It is a 39-amino acid synthetic peptide with agonist activity at both the GIP (glucose-dependent insulinotropic polypeptide) and GLP-1 receptors. Its structure is based on the GIP sequence and includes a C20 fatty di-acid moiety **CCI**. It is administered once-weekly (QW) by subcutaneous (SC) injection.

Study I8F-MC-GPHO (GPHO) is a phase 3, multicenter, randomized, open-label, parallel-group study to compare the efficacy and safety of 3 maintenance doses of tirzepatide with titrated insulin glargine in patients with T2DM naïve of insulin treatment who have inadequate glycemic control on stable doses of metformin with or without a sulfonylurea.

Objective(s)/Endpoints:

Objectives	Endpoints

Primary
 
 To demonstrate that once-weekly tirzepatide 10 mg and/or 15 mg is non-inferior to titrated insulin glargine as measured by change from baseline in hemoglobin A1c (HbA1c) at 40 weeks 	
 Mean change in HbA1c from baseline

Key Secondary (controlled for Type I error)
 
Efficacy
 
 To demonstrate that once-weekly tirzepatide 5 mg is noninferior to titrated insulin glargine for change from baseline in HbA1c at 40 weeks To demonstrate that once-weekly tirzepatide 5 mg, 10 mg, and/or 15 mg is superior in weight loss to titrated insulin glargine at 40 weeks To demonstrate that once-weekly tirzepatide 5 mg, 10 mg, and/or 15 mg is superior to titrated insulin glargine for change from baseline in HbA1c at 40 weeks To demonstrate that once-weekly tirzepatide 5 mg, 10 mg, and/or 15 mg is superior to titrated insulin glargine for the proportion of patients with HbA1c target value of <7.0% (53 mmol/mol) at 40 weeks 	
 Mean change in HbA1c from baseline Mean change in body weight from baseline Mean change in HbA1c from baseline Proportion of patients achieving HbA1c target of <7.0% (53 mmol/mol)

Additional Secondary (not controlled for type 1 error)
 
 To demonstrate that once-weekly tirzepatide 5 mg, 10 mg, and/or 15 mg is superior to titrated insulin glargine at 40 weeks for: To compare tirzepatide 5 mg, 10 mg, and 15 mg to titrated insulin glargine at 40 weeks for: 	
 Mean change in fasting serum glucose (central lab) from baseline Proportion of patients achieving an HbA1c target values of ≤6.5% (48 mmol/mol) and <5.7% (39 mmol/mol) Mean change in daily glucose average of 7-point self-monitored blood glucose (SMBG) profiles from baseline Proportion of patients who achieved weight loss ≥5%, ≥10%, and ≥15% from baseline Patient-reported outcomes: 
 Diabetes Treatment Satisfaction Questionnaire status/ Diabetes Treatment Satisfaction Questionnaire change

Objectives	Endpoints

Safety
 
 To compare tirzepatide 5 mg, 10 mg, and 15 mg to titrated insulin glargine for: 	
 Treatment-emergent adverse events (TEAEs) Early discontinuation of study drug due to adverse events (AEs) Adjudicated pancreatic AEs Serum calcitonin Incidence of allergic and hypersensitivity reactions Incidence of treatment-emergent anti-drug antibodies to tirzepatide Mean change in systolic and diastolic blood pressure and pulse rate from baseline Occurrence of hypoglycemic events Incidence of initiation of rescue therapy for severe persistent hyperglycemia

Summary of Study Design:

Study GPHO is a phase 3, multicenter, randomized, open-label, parallel-group study to compare the efficacy and safety of 3 maintenance doses of tirzepatide with titrated insulin glargine in patients with T2DM who have inadequate glycemic control on stable doses of metformin with or without a sulfonylurea (Figure GPHO.1).

Treatment Groups and Duration:

Study GPHO will consist of 3 periods: an approximately 3-week screening/lead-in period, followed by a 40 week treatment period, and a 4-week safety follow-up period. Patients will be randomized in a 1:1:1:1 ratio (tirzepatide 5 mg, 10 mg and 15 mg QW, and insulin glargine QD). Patients will be stratified at randomization based on HbA1c ($\leq 8.5\%$, $> 8.5\%$ [69 mmol/mol]), country and use of concomitant oral antidiabetic treatments (Metformin alone, metformin plus a sulfonylurea).

Number of Patients:

A total of approximately 956 patients will be randomized in a 1:1:1:1 ratio to tirzepatide doses: 5 mg QW (239 patients), 10 mg QW (239 patients), 15 mg QW (239 patients), and insulin glargine QD (239 patients).

Statistical Analysis:

Efficacy Analyses:

Efficacy and safety will be assessed using the modified intent-to-treat (mITT) population, which consists of all randomly assigned participants who are exposed to at least one dose of study drug. The primary efficacy assessment will be performed on data obtained before the initiation of any rescue therapy and before premature treatment discontinuation. The analysis model for change from baseline in HbA1c assessed over time will be a mixed-model for repeated measures (MMRM), with terms: treatment, visit, and treatment-by-visit interaction, stratification factors:

country and concomitant oral antidiabetic treatment (Metformin alone, metformin plus a sulfonylurea) as fixed effects, and baseline HbA1c as a covariate. An unstructured covariance structure will model relationship of within-patient errors.

Supportive analyses will be performed with the same MMRM model on per-protocol (PP) population and with an analysis of covariance (ANCOVA) model on mITT population. Details for the analysis conducted on PP population will be included in SAP. The ANCOVA analysis will be conducted using the Full Analysis Set (FAS), which consists of all available change from baseline in HbA1c data at week 40, irrespective of whether they were obtained while the participants had discontinued the investigational product or whether the participant had been given rescue medication. Additionally, data for subjects with missing values will be imputed based on observed data in the same treatment group from subjects who had their efficacy measure at the Week 40 visit assessed after early discontinuation of investigational product and/or initiation of rescue medication (retrieved drop outs). Analysis will be conducted with multiple imputations and statistical inference over multiple imputations will be guided by the method proposed by Rubin (Rubin 1987).

Additional details, including analysis methods for key secondary endpoints and a strategy for controlling overall family-wise Type 1 error rate at an alpha of 0.05 of primary and key secondary endpoint evaluation, will be provided in the statistical analysis plan (SAP).

Safety Analysis:

Safety assessment will be based on all available data including 4-week safety follow up period, irrespective of whether they were obtained while the participants had discontinued the study drug or whether the participant had been given rescue medication. Summary statistics will be provided for incidence of treatment-emergent adverse events (TEAEs), serious adverse events (SAEs), and study discontinuation due to adverse events (AEs) or deaths from the time of first dose through end of safety follow up. Counts and proportions of subjects experiencing AEs will be reported for each treatment group, and Fisher's exact test will be used to compare the treatment groups. For continuous laboratory analytes, summary statistics will be provided by visit, with statistical comparisons among treatment at each visit conducted using a mixed-model for repeated measures (MMRM) analysis. Selected safety analyses may be conducted excluding data after introducing another anti-hyperglycemic therapy (for example, rescue therapy)

Additional details, including analysis of adverse events of special interest, will be provided in the SAP.

2. Schedule of Activities

The Schedule of Activities described below should be followed for all patients enrolled in Study GPHO. However, for those patients whose participation in this study is affected by exceptional circumstances (rare events that may cause disruptions to the conduct of the study, such as pandemics or natural disasters), please refer to Appendix 7 for additional instructions.

Table GPHO.1. Schedule of Activities

	Study Period I		Study Period II																	Study Period III	
	Screening/ Lead in		Treatment Period																	Safety F/U	
Visit	1	2	3 ^a	4	5	6	7	8	9	10	11	12	13	14	15	16	17	18	19	ET ^b	801
Week of Treatment	-3	-2	0	1	2	3	4	5	6	7	8	10	12	14	16	20	24	32	40		4 weeks Post End of Tx
Allowable Deviation (days) ^c	-	±3	±7	±3	±3	±3	±3	±3	±3	±3	±3	±3	±3	±3	±3	±3	±3	±7	±7		±7
Fasting Visit ^d			X				X				X		X		X	X	X		X	X	X
Telephone Visit				X		X		X		X		X		X							
Informed consent	X																				
Randomization			X																		
Clinical Assessments																					
Medical history ^e	X																				
Physical examination	X																		X	X	
Height	X																				
Weight ^f	X		X				X				X		X		X	X	X	X	X	X	X
Waist circumference			X				X				X		X		X	X	X	X	X	X	X
Electrocardiogram			X																X	X	X
Vital signs (2 sitting BP and PR) ^g	X		X		X		X		X		X		X		X	X	X	X	X	X	X
Dilated Fundoscopic Examination ^h		X																			
Adverse events	X	X	X	X	X	X	X	X	X	X	X	X	X	X	X	X	X	X	X	X	X
Concomitant medications	X	X	X	X	X	X	X	X	X	X	X	X	X	X	X	X	X	X	X	X	X
Hypoglycemic events	X	X	X	X	X	X	X	X	X	X	X	X	X	X	X	X	X	X	X	X	X

	Study Period I		Study Period II																	Study Period III	
	Screening Lead in		Treatment Period																	Safety F/U	
Visit	1	2	3 ^a	4	5	6	7	8	9	10	11	12	13	14	15	16	17	18	19	ET ^b	801
Week of Treatment	-3	-2	0	1	2	3	4	5	6	7	8	10	12	14	16	20	24	32	40		4 weeks Post End of Tx
Allowable Deviation (days) ^c	-	±3	±7	±3	±3	±3	±3	±3	±3	±3	±3	±3	±3	±3	±3	±3	±3	±7	±7		±7
Fasting Visit ^d			X				X				X		X		X	X	X		X	X	X
Telephone Visit				X		X		X		X		X		X							
Patient Education																					
Diabetes education ^{i,j}		X																			
BG meter, SMBG training ^l		X																			
Dispense BG meter/supplies, as needed		X	X		X		X		X		X		X		X	X	X	X			
Study drug injection training ^j			X																		
Hand out diary, instruct in use ⁱ		X	X		X		X		X		X		X		X	X	X	X	X	X	X
Remind patients about 7-point SMBG ^k		X														X		X			
Review 7-point SMBG values collected in diary			X														X		X		
Dispense study drug			X				X				X		X		X	X	X	X			
Observe patient administer tirzepatide ^l			X																		

	Study Period I		Study Period II																	Study Period III	
	Screening Lead in		Treatment Period																	Safety F/U	
Visit	1	2	3 ^a	4	5	6	7	8	9	10	11	12	13	14	15	16	17	18	19	ET ^b	801
Week of Treatment	-3	-2	0	1	2	3	4	5	6	7	8	10	12	14	16	20	24	32	40		4 weeks Post End of Tx
Allowable Deviation (days) ^c	-	±3	±7	±3	±3	±3	±3	±3	±3	±3	±3	±3	±3	±3	±3	±3	±3	±7	±7		±7
Fasting Visit ^d			X				X				X		X		X	X	X		X	X	X
Telephone Visit				X		X		X		X		X		X							
Patient returns study drugs and injection supplies							X				X		X		X	X	X	X	X	X	X
Assess study drug compliance				X	X	X	X	X	X	X	X	X	X	X	X	X	X	X	X	X	X
Review insulin dose and adjustment per TTT algorithm ^m			X	X	X	X	X	X	X	X	X	X	X	X	X	X	X	X	X	X	X
Assess compliance with insulin dose adjustment TTT algorithm ^m					X		X		X		X		X		X	X	X	X	X	X	X

	Study Period I		Study Period II																	Study Period III	
	Screening Lead in		Treatment Period																	Safety F/U	
Visit	1	2	3 ^a	4	5	6	7	8	9	10	11	12	13	14	15	16	17	18	19	ET ^b	801
Week of Treatment	-3	-2	0	1	2	3	4	5	6	7	8	10	12	14	16	20	24	32	40		4 weeks Post End of Tx
Allowable Deviation (days) ^c	-	±3	±7	±3	±3	±3	±3	±3	±3	±3	±3	±3	±3	±3	±3	±3	±3	±7	±7		±7
Fasting Visit ^d			X				X				X		X		X	X	X		X	X	X
Telephone Visit				X		X		X		X		X		X							
Laboratory Tests																					
Serum pregnancy test ⁿ	X																				
Urine pregnancy test ^o			X										X				X		X		
Follicle-stimulating hormone test ^p	X																				
Chemistry panel	X ^q												X				X		X	X	X
Fasting serum glucose			X				X				X		X		X	X	X		X	X	X
Lipid panel			X																X	X	X
Urinary albumin/creatinine ratio	X ^q																		X	X	X
Serum creatinine, eGFR (CKD-EPI) ^r	X ^q												X				X		X	X	
Calcitonin	X ^q												X				X		X	X	X
Hematology	X ^q												X				X		X	X	X
HbA1c	X		X				X				X		X		X	X	X		X	X	X
Pancreatic amylase, lipase	X ^q												X				X		X	X	X
Immunogenicity ^s			X				X						X				X		X	X	X
PK sample for Immunogenicity ^t			X				X						X				X		X	X	X

	Study Period I		Study Period II																	Study Period III	
	Screening Lead in		Treatment Period																	Safety F/U	
Visit	1	2	3 ^a	4	5	6	7	8	9	10	11	12	13	14	15	16	17	18	19	ET ^b	801
Week of Treatment	-3	-2	0	1	2	3	4	5	6	7	8	10	12	14	16	20	24	32	40		4 weeks Post End of Tx
Allowable Deviation (days) ^c	-	±3	±7	±3	±3	±3	±3	±3	±3	±3	±3	±3	±3	±3	±3	±3	±3	±7	±7		±7
Fasting Visit ^d			X				X				X		X		X	X	X		X	X	X
Telephone Visit				X		X		X		X		X		X							
Anti-GAD antibody			X																		
Patient Reported Outcomes ^e																					
APPADL			X																X	X	
EQ-5D-5L			X																X	X	
IW-SP			X																X	X	
DTSQs			X																		
DTSQc																			X	X	

Abbreviations: APPADL = Ability to Perform Physical Activities of Daily Living; BG = blood glucose; BP = blood pressure; CKD-EPI = Chronic Kidney Disease-Epidemiology; DTSQc = Diabetes Treatment Satisfaction Questionnaire change; DTSQs = Diabetes Treatment Satisfaction Questionnaire status; eGFR = estimated glomerular filtration rate; EQ-5D-5L = European Quality of Life- dimensions; ET = early termination; F/U = follow-up; GAD = glutamic acid decarboxylase; HbA1c = hemoglobin A1c; PR = pulse rate; IW-SP = Impact of Weight on Self Perception; PK = pharmacokinetics; SMBG = self-monitored blood glucose; TTT = treat to target; Tx = treatment.

- ^a Baseline assessments must be completed before processing in the interactive web-response system.
- ^b Patients who are unable or unwilling to continue in the study for any reason will perform an ET visit. If the patient is discontinuing during an unscheduled visit, that visit should be performed as the ET visit. If the patient is discontinuing during a scheduled visit, that visit should be performed as an ET visit. Visit 801 (safety follow-up visit) should be performed 4 weeks after the ET visit as the final study visit.
- ^c The visit date is determined in relation to the date of the randomization visit (± the allowed visit window).
- ^d On visits 3, 7, 11, 13, 15, 16, 17, 19, ET, and at follow-up, patients should be reminded to report to the site in a fasting condition, after a period of approximately 8 hours without eating, drinking (except water), or any significant physical activity and before taking study drug(s), metformin and sulfonylurea (if used).
- ^e Medical history includes assessment of preexisting conditions (including history of gallbladder disease, cardiovascular disease, and medullary thyroid carcinoma) and substance usage (such as, alcohol and tobacco).

- ^f Weight measurements must be in kilograms.
- ^g Vital sign measurements should be taken before obtaining an ECG tracing and before collection of blood samples for laboratory testing, at visits where required. The participant should sit quietly for 5 minutes before vital sign measurements are taken. For each parameter, 2 measurements will be taken using the same arm; the recordings should be taken at least 1 minute apart. BP must be taken with an automated blood pressure machine.
- ^h Dilated fundoscopic examination will be performed for all patients between Visit 2 and Visit 3, unless there is a contraindication to dilate the eye (ie. closed angle glaucoma). The diagnosis will be made by an eye care professional (ophthalmologist or optometrist) before Visit 3 to exclude patients with proliferative diabetic retinopathy and/or diabetic maculopathy or nonproliferative diabetic retinopathy that requires acute treatment. The results from this examination will be recorded on a specific retinopathy eCRF as a baseline measure of retinopathy. Follow up dilated fundoscopic examination should be performed when clinically indicated, and the results recorded on the retinopathy eCRF.
- ⁱ Includes counseling on diet and exercise, symptoms and management of hypoglycemia, etc.
- ^j All training should be repeated as needed to ensure patient compliance.
- ^k Patient is required to collect two 7-point SMBGs on nonconsecutive days prior to the next visit. A 7-point SMBG consists of measurements before and 2 hours after each of 3 main meals within the same day and at bedtime. These SMBG profiles will be collected by the patient within 2 weeks prior to the assigned visits. If 7-point SMBG is not performed, then data from the most recent nonconsecutive 4-point SMBG (3 before each meal and one at bedtime) profiles can be used. If more than 2 SMBG profiles are available, the 2 most recent profiles on nonconsecutive days should be used. In the weeks that the 7-point profiles are performed, the 4-point SMBG profiles will not be needed.
- ^l Patients should administer their first dose of tirzepatide at the end of this visit, after all other study procedures and randomization.
- ^m During the first 8 weeks, the dose adjustment will be determined by the investigator in discussion with the patient by following a TTT algorithm. After Week 8, the dose adjustment will be determined by the patient in a weekly manner and will be reviewed by the investigator at each office visit. The dose adjustment will happen weekly during the first 16 weeks, and it is assumed that the dose will stay relatively stable from Week 16 onwards. Assessment of the patient's compliance to the TTT algorithm will be collected in the eCRF at Visits 7, 9, 11, 13, 15 and 19 for the period since the previous visit. PIs will be reminded that the review of dose is based on daily FBG.
- ⁿ A serum pregnancy test will be performed at Visit 1 for women of childbearing potential only. Females of childbearing potential are those who are not surgically sterilized and between menarche and 1-year postmenopausal.
- ^o A urine pregnancy test must be performed at Visit 3 with the result available prior to randomization and first injection of study drug(s) for women of childbearing potential only. Additional pregnancy tests will be performed at Visits 13, 17, and 19. Pregnancy tests may also be performed at the investigator's discretion during the study. If required per local regulations and/or institutional guidelines, pregnancy testing can also occur at other times during the study treatment period.
- ^p Follicle-stimulating hormone test performed at Visit 1 for potential postmenopausal women age 45 years or above with an intact uterus, not on hormone therapy or oral contraceptives, and who have had spontaneous amenorrhea for more than 6 months and less than 12 months and estradiol levels consistent with a postmenopausal state (FSH \geq 40 mIU/mL and estradiol <30 pg/mL).
- ^q Screening visit assessment will serve as baseline.
- ^r The CKD-EPI equation will be used by the central lab to estimate and report eGFR.
- ^s In the event of systemic drug hypersensitivity reactions (immediate or nonimmediate), additional blood samples will be collected including ADA, PK, and an exploratory immune safety sample.
- ^t PK samples for immunogenicity must be taken prior to drug administration.
- ^u All PROs should be completed before any other study procedures if the patient is not adversely affected by the fasting condition or completed after the patient has sufficiently recovered from the preceding visit procedures.

Note: Patients will be encouraged to collect a daily fasting BG and a weekly 4-point SMBG. Missing a fasting BG measurement will not be considered a protocol deviation.

3. Introduction

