
Additional Secondary (not controlled for type 1 error) Efficacy
 
 To demonstrate that once-weekly tirzepatide 5 mg, 10 mg, and/or 15 mg is superior to titrated insulin glargine at 40 weeks for: To compare tirzepatide 5 mg, 10 mg, and 15 mg to titrated insulin glargine at 40 weeks for 	
 Mean change in FSG (central lab) from baseline Proportion of patients achieving an HbA1c target values of ≤6.5% (48 mmol/mol) and <5.7% (39 mmol/mol) Mean change in daily glucose average from 7-point SMBG profiles from baseline Proportion of patients who achieved weight loss ≥5%, ≥10%, and ≥15% from baseline Patient-reported outcomes: 
 Diabetes Treatment Satisfaction Questionnaire status/ Diabetes

Objectives	Endpoints
	Treatment Satisfaction Questionnaire change

Safety
 
 To compare tirzepatide 5 mg, 10 mg, and 15 mg to titrated insulin glargine for: 	
 TEAEs Early discontinuation of study drug due to AEs Adjudicated pancreatic AEs Serum calcitonin Incidence of allergic and hypersensitivity reactions Incidence of treatment-emergent anti-drug antibodies to tirzepatide Mean change in systolic and diastolic blood pressure and pulse rate from baseline Occurrence of hypoglycemic events Incidence of initiation of rescue therapy for severe persistent hyperglycemia

Exploratory
 
 To compare tirzepatide 5 mg, 10 mg, and 15 mg to titrated insulin glargine with respect for the following: 	
 Change in lipids (total cholesterol, HDL, VLDL, and TG) Changes from baseline in mean body mass index (BMI) Mean change in waist circumference European Quality of Life- dimensions (EQ-5D-5L) scores Impact of Weight on Self Perception Ability to Perform Physical Activities of Daily Living

Abbreviations: HDL=high density lipoprotein; TG = triglycerides; VLDL = very low density lipoprotein

5. Study Design

[figure not shown]

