Patients will also be required to collect a weekly 4-point SMBG. These 4-point SMBG profiles should include fasting (or pre-morning meal), pre-midday meal, pre-evening meal, and bedtime values. In the weeks that the 7-point profiles are performed, the 4 –point SMBG profiles will not be needed.

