6.4. Handling of Dropouts or Missing Data

For analyses using in EAS, missing data will be addressed by using a mixed-effect model repeated measures (MMRM) analysis for continuous longitudinal variables. The MMRM model provides consistent estimator when data is missing at random. The model implicitly adjusts for missing data through a variance-covariance structure. For health outcomes data, LOCF will be used for Analysis of Covariance (ANCOVA) analysis and item-level missingness is dealt with as per instrument developers' instruction.

For analyses using FAS, data for patients with missing values at the 40-week visit will be imputed based on the method described in Section [6.12.1.3](#). Unless specified otherwise, imputation of missing data will be limited to primary and key secondary efficacy endpoint analyses.

Missing other secondary or exploratory efficacy parameter values and missing safety laboratory values will not be explicitly imputed.

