6.12.4. Other Secondary and Exploratory Efficacy Analyses

Other secondary and exploratory efficacy measures will be summarized by treatment and nominal visit. Statistical analyses will be conducted in a manner similar to Sections 6.12.1 and 6.12.2.

Table GPHO.6.2. Secondary and Exploratory Efficacy Measures Not Controlled for Type 1 Error

Objective	Relative to the efficacy measure:	Analysis Conducted in a manner similar to:	Additional Information
Secondary Analyses			
once-weekly tirzepatide 5 mg, 10 mg, and/or 15 mg is superior to insulin glargine at 40 weeks	Change from baseline in fasting serum glucose (central laboratory)	6.12.1.1	Use baseline HbA1c strata as a fixed effect in place of baseline HbA1c as a covariate. Use baseline FSG as a covariate. LSM estimates will be plotted by treatment and visit.
	Proportion of patients achieving an HbA1c target value of $\leq 6.5\%$ (48 mmol/mol),	6.12.2.3	None
	Proportion of patients achieving an HbA1c target value of $< 5.7\%$ (39 mmol/mol).	6.12.2.3	None
	Change from baseline in 7-point self-monitored blood glucose (SMBG) profiles	6.12.1.1	Use baseline HbA1c strata as a fixed effect in place of baseline HbA1c as a covariate. Use baseline SMBG as a covariate. LSM estimates at 40-weeks will be plotted by treatment and 7-points. In addition to the analyses on each of the 7-points, similar analyses will be done for the 2-hour morning, midday, and evening meal excursions, the mean of all meals 2-hour excursion, the mean of all 7-point measurements, the mean of all pre-meal measurements, and the mean of all 2-hour postprandial measurements.
	Proportion of patients achieving weight loss of $\geq 5\%$, from baseline	6.12.2.3	Use baseline HbA1c strata as a fixed effect in place of baseline HbA1c as a covariate and baseline weight as a covariate

	Proportion of patients achieving weight loss of $\geq 10\%$ from baseline	6.12.2.3	Use baseline HbA1c strata as a fixed effect in place of baseline HbA1c as a covariate and baseline weight as a covariate
	Proportion of patients achieving weight loss of $\geq 15\%$ from baseline	6.12.2.3	Use baseline HbA1c strata as a fixed effect in place of baseline HbA1c as a covariate and baseline weight as a covariate

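### The protocol lets 4-point profiles, which have no post-meal readings, stand in for 7-point SMBG profiles, and the SAP does not say whether they enter the 7-point daily mean

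*Protocol*

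**What the plan says.** Footnote k to the Schedule of Activities (Protocol Section 2) defines the full profile: "A 7-point SMBG consists of measurements before and 2 hours after each of 3 main meals within the same day and at bedtime". Two such profiles are to be collected on nonconsecutive days in the two weeks before Visit 3 (baseline), Visit 17 (Week 24) and Visit 19 (Week 40). The same footnote gives the fallback: "If 7-point SMBG is not performed, then data from the most recent nonconsecutive 4-point SMBG (3 before each meal and one at bedtime", and continues that these profiles can be used. It then says: "If more than 2 SMBG profiles are available, the 2 most recent profiles on nonconsecutive days should be used". That sentence does not say which type of profile it means.

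Protocol Section 5.1 describes the shorter profile: "These 4-point SMBG profiles should include fasting (or pre-morning meal), pre-midday meal, pre-evening meal, and bedtime values". It is planned weekly for every patient.

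The endpoint in Protocol Section 4, Table GPHO.2, is "Mean change in daily glucose average from 7-point SMBG profiles from baseline", listed under "Additional Secondary (not controlled for type 1 error"). SAP Table GPHO.6.2 (Section 6.12.4) sends the 7-point profile to the MMRM of Section 6.12.1.1. It analyses each of the seven points, the 2-hour meal excursions, the pre-meal and post-meal means, and "the mean of all 7-point measurements". SAP Section 6.4 adds: "Missing other secondary or exploratory efficacy parameter values and missing safety laboratory values will not be explicitly imputed". The SAP has no rule for 4-point profiles, for a minimum number of points, or for combining the two types.

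**The concern.** A daily mean over three pre-meal, three post-meal and one bedtime value is a different quantity from a mean over three pre-meal values and one bedtime value. If the second is entered as if it were the first, the change from baseline picks up a difference between measurement schemes whenever substitution is not balanced across visits.

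Because 4-point profiles are collected weekly, a substitute will usually be available. Read literally, the sentence on the two most recent profiles could even let a later 4-point profile displace a completed 7-point one. Footnote k limits this by waiving the 4-point profile in weeks when 7-point profiles are done, but the collection window is two weeks.

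Excursions and post-meal means cannot be computed from a 4-point profile, so the daily mean and its components could rest on different patients. Two programmers following the documents could produce different results. What is at stake is the interpretation of this one endpoint and its components. No primary or key secondary endpoint uses SMBG profiles.

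**Working it through.** The documents give no expected value, variance or power for the SMBG endpoint, so there is no planned figure to reproduce. The check is algebra on the two profile definitions. All glucose values and substitution rates below are assumptions, because the documents give none.

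**Visit mean.** Let P be the mean of the three pre-meal values, P + e the mean of the three post-meal values, and P + b the bedtime value.

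- 7-point mean = [3P + 3(P + e) + (P + b)]/7 = P + (3e + b)/7
- 4-point mean = [3P + (P + b)]/4 = P + b/4
- Difference (4-point minus 7-point) = b/4 - b/7 - 3e/7 = -(3/7)(e - b/4)

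The difference is negative when e > b/4. For e = 1 to 3 and b = 0 to 1 mmol/L:

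- smallest (e = 1, b = 1): -(3/7)(0.75) = -0.32 mmol/L
- largest (e = 3, b = 0): -(3/7)(3) = -1.29 mmol/L
- one of two equally weighted profiles substituted: half, -0.16 to -0.64 mmol/L

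The sign is not guaranteed. With e = 10 mg/dL, the difference is 0.0 at b = 40 mg/dL and -(3/7)(10 - 15) = +2.1 mg/dL at b = 60 mg/dL.

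**Change from baseline.** Write d = (3/7)(e - b/4) at each visit, with shares p0 and p1 of patients fully substituted at baseline and Week 40. The bias in mean change (Week 40 minus baseline) is p0·d0 - p1·d1. Assume e = 60 mg/dL at baseline, 30 mg/dL at Week 40, and b = 20 mg/dL at both:

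- d0 = (3/7)(60 - 5) = 23.6 mg/dL; d1 = (3/7)(30 - 5) = 10.7 mg/dL
- 10% substituted at Week 40 only: -1.1 mg/dL (reduction exaggerated)
- 10% at baseline only: +2.4 mg/dL (reduction understated)
- 10% at both visits: +2.36 - 1.07 = +1.3 mg/dL (partial cancellation, net understatement)
- 10% at baseline and 30% at Week 40: +2.36 - 3.21 = -0.9 mg/dL

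**Between arms.** Two illustrations, both with substitution at Week 40 only:

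- If one arm substitutes 10 percentage points more often and d is the same in both arms, the contrast moves by 0.10 × 0.32 to 0.10 × 1.29, or 0.03 to 0.13 mmol/L.
- If both arms substitute at the same rate p but their post-meal rises differ, with equal b, the contrast (tirzepatide minus glargine) moves by -p(3/7)(e_T - e_G). At p = 10% and an assumed rise 1 mmol/L lower on tirzepatide, this is +0.10 × 0.43 = +0.04 mmol/L, which understates the tirzepatide advantage.

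Unequal rates can therefore push the contrast either way, and equal rates do not remove the problem.

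**The case against.** The strongest reply is that the substitution may never reach the analysis. Footnote k is permissive and does not name the daily-average endpoint. The SAP's variable is the mean of all seven points, which a 4-point profile cannot supply, and SAP Section 6.4 rules out explicit imputation for this class of endpoint. The eCRF instruction in Protocol Section 5.1 names only the 7-point values. On that reading the SAP already treats such visits as missing. This has force: a reader might infer that 4-point data will enter the analysed mean, and the documents do not establish that. It does not close the matter. The protocol allows the substitution, the evident use of the 7-point profiles is this endpoint and its components, the SAP does not exclude the rule, and Protocol Appendix 3.2.1 provides for transcribing diary data generally.

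A second reply is that the fallback reduces missing data, and that treating those visits as missing relies on missing at random, which uneven patient diligence would also strain. That is true. The MMRM assumption is at least stated and can be examined, whereas a mean with an undeclared mixture of definitions cannot be interpreted.

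A third is that substitution should be uncommon, given the scheduled reminders at Visits 2, 16 and 18 and the review of values at Visits 3, 17 and 19. That may be so, but the documents give no rate.

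**Conclusion.** The point stands as a gap between a protocol allowance and the SAP, of minor consequence. A fully substituted visit mean differs from the 7-point mean by -(3/7)(e - b/4), normally downward: -0.3 to -1.3 mmol/L under the assumed rises, and half that when one of two profiles is replaced.

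Two stronger readings are tempting and are not supported. One is that every substitution lowers the mean. It does so only when e > b/4, which is likely on average but not certain. The other is that the endpoint is biased in a known direction or in favour of one arm. Substitution at Week 40 exaggerates the reduction, substitution at baseline understates it, and substitution at both partly cancels or reverses. The between-arm effect depends on substitution rates and post-meal rises by arm, which the documents do not give. The 0.03 to 0.13 mmol/L figure is illustrative and holds only for an assumed 10-point imbalance at Week 40 alone with full substitution. The endpoint is an additional secondary one without type 1 error control.

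**What to change.** Add a short rule to the SAP beside the SMBG row of Table GPHO.6.2:

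- Only 7-point profiles feed the 7-point mean, the post-meal means and the excursions.
- 4-point profiles may contribute only to the separate pre-meal and bedtime points, and must not displace a completed 7-point profile.
- A visit without a 7-point profile is missing for the 7-point mean and is left to the MMRM already specified.

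If the sponsor prefers to keep the substitution, the SAP should say so, report its frequency by arm and visit, and add a sensitivity analysis limited to patients with 7-point profiles at both baseline and Week 40.

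The cost is a few sentences and slightly more missing data on this endpoint. Missing post-baseline visits are handled under missing at random. A missing baseline is different: SAP Section 6.2 requires both a baseline and a post-baseline value, so a patient with no baseline 7-point profile would drop out of this change analysis.
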